6.3 Duration of Treatment for Each Patient at Each Cohort

Twelve cycles of treatment is recommended for patients who have a response, unless or until:

- Patients exhibit progression of disease together with worsening of biliary function, no longer meeting eligibility criteria, or exhibiting symptomatic progression; or patients exhibit progression of disease which was confirmed after 1 additional treatment cycles
- Unacceptable toxicity from CPI-613
- Patient withdrawal of consent

Comprehensive Cancer Center of Wake Forest University
A Pilot Study: Open-Label Clinical Trial of CPI-613 in Patients with Advanced Bile Duct
Cancers
CCCWFU # 59212

- Investigator's discretion to withdraw patients from the study because continued participation in the study is not in the patient's best interest.
- Undercurrent illness: a condition, injury, or disease unrelated to the intended disease for which the study is investigating, that renders continuing the treatment unsafe or regular follow-up impossible
- General or specific changes in the patient's condition that renders the patient ineligible for further investigational treatment
- Non-compliance with investigational treatment, protocol-required evaluations or follow-up visits
- Termination of the clinical trial by the sponsor

When terminating treatment during this trial, the investigator should make every effort to contact the patient and to perform a final evaluation. Also, the reason(s) for withdrawal from the study must be recorded.

All patients will be followed until death.

Additional treatment cycles beyond the recommended 12 cycles can be given if the investigator considers it beneficial to do so.

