Comprehensive Cancer Center of Wake Forest University
A Pilot Study: Open-Label Clinical Trial of CPI-613 in Patients with Advanced Bile Duct
Cancers
CCCWFU # 59212

Principal Investigator: [name] [name]
Section on Hematology and Oncology
Wake Forest School of Medicine
[name]
[name]

Co-Investigators: A. [name]
Department of Radiation Oncology
Wake Forest School of Medicine

Biostatistician: [name], PhD
Division of Public Health Sciences
Comprehensive Cancer Center of Wake Forest University

Research Nurse: [name] [name]
Comprehensive Cancer Center of Wake Forest University

Data Manager: [name]
Comprehensive Cancer Center of Wake Forest University

Regulatory / Budget: [name]
Comprehensive Cancer Center of Wake Forest University

Investigational Drug: CPI-613

IND Number: 117,500

Drug Sponsor: Cornerstone Pharmaceuticals, Inc.

Version Date: 07.16.18
02.28.18
02.22.17
02.16.16
10.22.15
06.16.15

Comprehensive Cancer Center of Wake Forest University
A Pilot Study: Open-Label Clinical Trial of CPI-613 in Patients with Advanced Bile Duct
Cancers
CCCWFU # 59212

[figure not shown]
04.23.15
01.21.15
11.14.14
09.08.14
07.24.14
06.19.14
05.20.14
02.28.14
08.16.13
07.16.13
04.23.13
04.05.13
02.08.13
02.04.13
12.19.12

Proprietary and Confidential

SCHEMA

Patients with histologically
and cytologically proven
bile duct cancer

Comprehensive Cancer Center of Wake Forest University
A Pilot Study: Open-Label Clinical Trial of CPI-613 in Patients with Advanced Bile Duct
Cancers
CCCWFU # 59212

Primary Objective

To evaluate the safety and anti-cancer activities (assessed based on Response Rate) of CPI-613 in patients with advanced unresectable bile duct cancer who have failed available therapies.

Secondary Outcome measures

- Progression-free survival
- Overall Survival

Design

Open-label single arm

* Maximum number of cycles allowed is 12, unless the investigator considers additional treatment can provide clinical benefit

** Two additional cycles will not be given if the patient no longer meets eligibility criteria, has worsening of biliary function, or has symptomatic progression.

Comprehensive Cancer Center of Wake Forest University
A Pilot Study: Open-Label Clinical Trial of CPI-613 in Patients with Advanced Bile Duct
Cancers
CCCWFU # 59212

Table of Contents

1. BACKGROUND AND STUDY OBJECTIVES.....	6
2. STUDY DESIGN.....	7
2.1 Study Objective.....	7
2.2 Outcome Measures.....	7

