CPI-613 is a novel anti-cancer agent (Zachar et al. 2011). CPI-613 selectively targets the altered form of mitochondrial energy metabolism in tumor cells, causing changes in mitochondrial enzyme activities and redox status which leads to apoptosis, necrosis and autophagy of tumor cells (Zachar et al. 2011). The activities of CPI-613 involve the catalytic and regulatory functions of the altered form of the pyruvate dehydrogenase complex (PDC) and the α -ketoglutarate dehydrogenase complex (KGDHC) found in tumor cells (Zachar et al. 2011). CPI-613 is also well-tolerated at doses up to 3,000 mg/m², according to Phase 1 trials in patients with solid tumors and hematologic malignancies. Although it has not been investigated in patients with cholangiocarcinoma, CPI-613 has exhibited anti-cancer activities against a variety of advanced cancers including different types of solid tumors (Lee et al. 2011 & 2012; Senzer et al. 2012) and hematologic malignancies (Pardee et al, 2011a and b, & 2012). Therefore, the anti-cancer activities and safety of CPI-613 against advanced bile duct cancers are investigated in this study. Interestingly, after the first two cycles of treatment, the radiologic response by CAT scan or PET scan did not correlate well with the clinical response for various tumor types, and patients had increased survival despite pseudo-progression on their initial scan. One of the reasons is that CPI-613 seems to be producing an inflammatory and necrotic local effect that can

Comprehensive Cancer Center of Wake Forest University
A Pilot Study: Open-Label Clinical Trial of CPI-613 in Patients with Advanced Bile Duct
Cancers
CCCWFU # 59212

be read as pseudo-progression on a standard CT. For this reason, we will allow patients to continue for an additional two cycles even if the first treatment scan shows progression of disease by RECIST criteria. After 2 additional cycles, we expect to understand if the patient responded to therapy or not as the inflammatory/necrotic effect should have subsided. Allowing 2 additional treatment cycles with Disease Progression according to RECIST cannot take place if any of the following conditions occur:

- the patient no longer meets eligibility criteria set at the start of the protocol (see Section 3.)
- worsening of biliary function when compared to baseline
- the patient has symptomatic progression

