According to the Response Evaluation Criteria in Solid Tumors (RECIST), the efficacy of treatment for solid tumors is determined by the tumor size. RECIST criteria are the golden standard to evaluate the tumor. In this study RECIST criteria will be used to evaluate response. However, there is a *pseudoprogression* phenomenon described with the use of CPI-613 in Phase I solid tumor studies (Lee et al. 2012).

It is felt that if CPI-613-induces necrosis of the tumor lesion there may be some radiographic evidence for increasing size. CPI-613 induces tumor necrosis due to its mechanism of action – selectively targeting the altered form of mitochondrial energy metabolism in tumor cells, causing changes in mitochondrial enzyme activities and redox status, which leads to apoptosis, necrosis, and autophagy of tumor cells (2,3,7,17,18).

For the purposes of this study, pseudoprogression will be defined and considered in patients who meet RECIST criteria of progression. It will be the treating physician's discretion to continue treatment in this situation if the patient is deemed to be getting clinical palliative benefit. In these patients, the study drug can be given for another two cycles prior to making definitive determination of progression or response.

Assessment of tumor response will be the responsibility of the principal investigator and should be based on radiologic findings (i.e., contrast CT of the chest, abdomen, and pelvis, and MRI of the abdomen), CA-19-9 and performance status.

OS will be monitored bimonthly via telephone contact after treatment termination. (**Note:** During the bimonthly post-study telephone contact, information related to cancer treatment received after the study will also be collected). OS and PFS will be calculated from the first day of treatment. The duration of OS will be measured until the date of death or censored at follow-up. The duration of response (evaluated by PFS) will be measured from the date a first objective response is documented until the first sign of progression assessed by MRI and CT.

****NOTE:** Tumor necrosis alone should not be criteria for determining

Comprehensive Cancer Center of Wake Forest University
A Pilot Study: Open-Label Clinical Trial of CPI-613 in Patients with Advanced Bile Duct
Cancers
CCCWFU # 59212

progression.

Safety and RR of CPI-613 are the primary endpoints, whereas PFS and OS are secondary endpoints.

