Pseudoprogession will be ruled out by allowing patients to receive the study drug for another 2 cycles after the first response assessment before making definitive assessment of progression or response. However, patients will not be allowed to continue treatment with CPI-613 at the time of “pseudo-progression” if any of the following criteria are met:

- a. The patient does not meet eligibility criteria set at the start of the protocol.
- b. Biliary function worsens.
- c. The patient has symptomatic progression.

OS will be determined from the first dose of CPI-613 to death, assessed up to 3 years after the first dose of CPI-613. Post-study survival, medical and cancer treatment information will be collected bimonthly via telephone contact after treatment termination.

RR is defined as % of patients who experienced a Complete Response (CR) or Partial Response (PR). CR and PR are based on Response Evaluation Criteria in Solid Tumor (RECIST) Version 1.1 Eisenhauer et al. 2009). The best response recorded from the start of the treatment until Disease Progression (DP) will be considered.

PFS will be determined from the first dose of CPI-613 to DP or death due to any cause, assessed up to 3 years after the first dose of CPI-613.

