Appendix E – Withdrawal of Participation Form

ORIS PID _____

Date Completed ____ / ____ / ____

Name of person completing form _____

Did the subject meet eligibility criteria for study enrollment? Yes No

Was the subject withdrawn from the study? Yes No

Reasons for withdrawal: (Check all that apply and provide additional information)

- Patient exhibited progression of disease
 - Patient exhibited progression of disease together with worsening of biliary function
 - Exhibiting symptomatic progression
 - Patient exhibit progression of disease which was confirmed after 2 additional treatment cycles
- Unacceptable toxicity from CPI-613
- Patient withdrawal of consent
 - For just the primary intervention (CPI-613 administration only)
 - For all components of the research study (including follow up in the medical record)
- Investigator's discretion to withdraw patient from the study because continued participation in the study is not in the patient's best interest
- Undercurrent illness: a condition, injury, or disease unrelated to the intended disease for which the study is investigating, that renders continuing the treatment unsafe or regular follow-up impossible
- General or specific changes in the patient's condition that renders the patient ineligible for further investigational treatment
- Non-compliance with investigational treatment, protocol-required evaluations or follow-up visits
- Termination of the clinical trial by the clinical sponsor

COMMENTS: _____

Comprehensive Cancer Center of Wake Forest University
A Pilot Study: Open-Label Clinical Trial of CPI-613 in Patients with Advanced Bile Duct
Cancers
CCCWFU # 59212

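### Section 6.3 ends treatment on progression confirmed after 1 additional cycle; every other statement of the number, and the scan schedule, says 2

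*Combined protocol and SAP*

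**What the plan says.** Section 6.3 lists the events that end treatment. One of them is "progression of disease which was confirmed after 1 additional treatment cycles".

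The other places that give a number of additional cycles are these:

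- Schema, second footnote: "Two additional cycles will not be given if the patient no longer meets eligibility criteria", followed by the two other conditions that bar continuation.
- Section 1: patients may "continue for an additional two cycles even if the first treatment scan shows progression of disease by RECIST criteria". The reason follows: "After 2 additional cycles, we expect to understand if the patient responded to therapy or not as the inflammatory/necrotic effect should have subsided". The sentence introducing the conditions that bar continuation again gives the number as 2.
- Section 5.1.3, where pseudoprogression is defined: "the study drug can be given for another two cycles prior to making definitive determination of progression or response". The choice is left to the treating physician's "discretion to continue treatment in this situation if the patient is deemed to be getting clinical palliative benefit".
- Section 5.1.3, later: pseudoprogression is ruled out by "allowing patients to receive the study drug for another 2 cycles after the first response assessment".
- Appendix E, withdrawal form: "progression of disease which was confirmed after 2 additional treatment cycles".

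Table 5-2, footnote 4, sets the first on-treatment CT in week 4 of cycle 3 for all patients. If that scan shows progression, the next is in week 4 of cycle 5.

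Section 5.1.3 also contains a sentence with no number. If the principal investigator finds progression at the assessment after the first three cycles, the patient comes off study.

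**The concern.** The additional cycles are the protocol's means of telling pseudoprogression from true progression. Section 1 gives a reason for two of them: the local inflammatory and necrotic effect on the scan is expected to have cleared by then. Section 6.3 sets a different threshold in the list a site would consult when deciding whether to stop. Taken literally, it supports calling progression one cycle before the point at which the protocol expects the picture to be readable, and at a time when no scan is planned.

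RR is a primary outcome and PFS a secondary one, and both depend on when progression is declared. There is also a record-keeping mismatch. A stop made under Section 6.3 after one additional cycle would not fit the confirmed-progression item in Appendix E, which specifies two.

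**Working it through.** This is a consistency check by counting. No power or sample-size formula applies.

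**1. Count of statements giving a number of additional cycles.**

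- Saying 2: schema footnote (1), Section 1 (3), Section 5.1.3 (2), Appendix E (1). Total 1 + 3 + 2 + 1 = 7.
- Saying 1: Section 6.3 (1).

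The Appendix E item is almost the same sentence as the Section 6.3 bullet, with 2 in place of 1. The plural noun after the 1 in Section 6.3 also points to an editing slip.

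**2. What the scan schedule implies (Table 5-2, footnote 4).**

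- Additional cycles = cycle of the repeat scan - cycle of the first scan = 5 - 3 = 2.
- Section 6.3 would put confirmation at cycle 3 + 1 = 4, where no scan is scheduled. Its figure of 1 cannot be reproduced from the schedule.
- With 2 in Section 6.3, confirmation falls at cycle 3 + 2 = 5, which matches footnote 4.

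**3. Size of the difference.** Inputs from Section 6.0: a cycle is 4 weeks, with two infusions a week in the first three weeks.

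- Infusions per cycle: 2 x 3 = 6.
- Two additional cycles: 2 x 4 = 8 weeks and 2 x 6 = 12 planned infusions.
- One additional cycle: 4 weeks and 6 planned infusions.
- Difference: 8 - 4 = 4 weeks and 12 - 6 = 6 infusions.

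Six is an upper limit on the infusions lost, because doses can be withheld under Section 6.2.

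**4. Timing, without dosing delays.**

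- Cohort 1 (no pre-cycle week): first scan in week 3 x 4 = 12, repeat scan in week 5 x 4 = 20. The last infusion is in week 12 + 3 = 15 after one additional cycle, or week 16 + 3 = 19 after two.
- Later cohorts (add the one-week pre-cycle): scans in weeks 13 and 21, last infusion in week 16 or week 20.

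**5. Who could be affected.** Only patients who progress on the cycle 3 scan, are not barred from continuing (still eligible, biliary function no worse, no symptomatic progression), whose physician chooses to continue, and whose progression is then confirmed before the cycle 5 scan. On the planned schedule no CT would prompt that, so the loss is 0 unless there is an unscheduled scan or a clinical judgement after cycle 4.

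**6. The removal sentence in Section 5.1.3.** Read plainly, it allows 0 additional cycles after progression at the first assessment. The two statements quoted from the same section allow 2. It gives no number, so it does not alter the count in step 1, but it conflicts with the same allowance.

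**The case against.** The strongest reply is that this is a one-character slip with no practical effect. The intended number is clear from everything else, the form on which withdrawal is recorded already has it, and the planned scan falls in cycle 5. The lead-in to Section 6.3 is a recommendation about twelve cycles for patients who respond, so read literally it hardly addresses a patient who progressed at cycle 3. The same list lets the investigator withdraw a patient in the patient's best interest, and Section 5.1.3 leaves continuation to the treating physician. Anyone wishing to stop after cycle 4 could already do so.

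Most of this stands as to size. It does not make the figure right. Section 6.3 is where discontinuation reasons are listed, and its number contradicts the rationale in Section 1.

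A reader might infer more than the documents support in two ways:

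- **That patients will lose a cycle they are entitled to.** They will not on the planned schedule, and continuation is discretionary rather than an entitlement.
- **That the allowance covers only the first scan, with CT as the sole confirmation, and that Section 6.3 should say so.** Section 1 and one statement in Section 5.1.3 speak of the first scan or assessment, and the Appendix D form offers pseudo-progression for the first CT only. But the definition in Section 5.1.3 and the schema footnote carry no such limit, and no text expressly bars later scans. Section 5.1.3 also bases response on MRI, CA-19-9 and performance status as well as CT. Either addition would be a new restriction.

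**Conclusion.** The point holds as an internal inconsistency: Section 6.3 says 1 where the protocol elsewhere says 2 and schedules for 2. It is worth correcting because it sits in the discontinuation list, but the consequence is small. The loss is nil if confirmation waits for the scheduled cycle 5 CT. It is at most one cycle, 4 weeks and up to 6 infusions, if a site confirms progression after cycle 4. That upper figure assumes the patient would otherwise have completed the second additional cycle.

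A reader might go on to infer that RR or PFS will be biased. The documents do not support a figure or a direction. They do not say how many patients would continue past progression at cycle 3, or how often a site would assess them outside the schedule.

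The removal sentence in Section 5.1.3 is a related conflict with the same allowance, and correcting Section 6.3 alone would leave it in place.

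**What to change.** In Section 6.3, change the number of additional treatment cycles from 1 to 2. Optionally add a cross-reference to the week 4, cycle 5 scan in Table 5-2, footnote 4.

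In Section 5.1.3, make the sentence that removes patients with progression at the first assessment subject to the two-cycle allowance described later in that section.

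Do not use this amendment to exclude progression first seen on later scans or to require confirmation by CT alone.

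The cost is a wording amendment to one bullet and one sentence. No scheduled scan or procedure and no sample size changes. The schema, Section 1, Table 5-2 and Appendix E need no change on the cycle count.

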7.0 STUDY DRUG - CPI-613

7.1 Description of CPI-613 Drug Product

CPI-613 is provided in 10-mL amber glass vials. Each vial contains 10 mL of CPI-613 at a concentration 50 mg/mL, equivalent to 500 mg of CPI-613. The drug product of CPI-613 is a clear and colorless solution that is free of any particulate matter.

7.2 Handling of CPI-613

CPI-613 is an investigational drug and its toxicity in humans is not fully understood. All necessary precautions in handling potentially toxic chemicals must be strictly adhered to. Gloves and protective clothing must be worn when handling CPI-613. Avoid contact by all modes of exposure. If the solution contacts the skin, it must be washed immediately and thoroughly with soap and water. If the solution comes in contact with mucous membranes, the membranes must be flushed thoroughly with water. Spills should be picked up with absorbent material and the area must be washed at least 3 times with ethyl alcohol followed by water.

CPI-613 drug product is slightly photosensitive (Study# PHO-001). Therefore, after removal of CPI-613 drug product from the amber vials, CPI-613 drug product should be protected from excessive light before administration to patients.

Comprehensive Cancer Center of Wake Forest University
A Pilot Study: Open-Label Clinical Trial of CPI-613 in Patients with Advanced Bile Duct
Cancers
CCCWFU # 59212

7.3 Storage of CPI-613

CPI-613 should be stored under refrigeration, at 2°-8°C (36°-46°F), except when being prepared for administration.

7.4 Intravenous (IV) Infusion Sets, Syringes and IV Bags to be Used for Administration of CPI-613

CPI-613 must be administered IV by infusion, via an IV catheter with D5W running at a rate of about 125-150 mL/hr. To avoid local reactions at and around the site of administration, CPI-613 should be administered via a central venous catheter. Subsequent sections describe the appropriate types of IV catheters, IV bags, syringes and clinical solutions that can be used in mixing and administering CPI-613 to patients.

Leaching of Diethylhexyl Phthalate (DEHP): CPI-613 can cause leaching of DEHP from IV infusion sets and IV bags (Study COM-003). Therefore, DEHP-containing IV infusion sets, IV bags or syringes should not be used in mixing or administration of CPI-613. Examples of the IV sets, IV bags and syringes that do not contain DEHP and therefore can be used in the administration of CPI-613 are:

Extension Set for Syringe Pump Use: All extension sets from MED-RX do not contain DEHP.

Syringes: Kendall Monoject syringes, all mono-ject syringes are DEHP free.

IV Infusion Sets: A compatibility study has been conducted showing that CPI-613 is compatible with 4 commonly used IV infusion sets (Study# COM-001). Therefore, these 4 types of IV infusion sets, and IV infusion sets that are made with the same materials, can be used to administer CPI-613. These IV infusion sets are:

- PVC material - ADDitIV® Primary IV Set with Universal Spike, Backcheck Valve, 2 Injection Sites, DEHP-Free and Latex-Free, 15 drops/mL, REF V14453, B Braun Medical Inc.
- Latex material - Interlink® System Secondary Medication Set, 10 drops/mL, 2C7451, Baxter Healthcare Corporation
- PVC material - Surshield™ Safety Winged Infusion Set, 0.19 mL Volume, Latex-Free, DEHP-Free, SV*S25BLS, Terumo Medical Products Hangzhou Co. Ltd.
- Polyethylene material - Interlink® System Paclitaxel Set by Baxter HealthCare, Non DEHP-free: Polyethylene tubing with a 0.22 microfilter Item # 2C7558 10 drops/mL

Syringes: Compatibility studies (Studies# COM-001 and COM-002) have shown that CPI-613 drug product (50 mg/mL), and drug product diluted with D5W to various concentrations (1.6-25 mg/mL) are compatible with various types of syringes, as listed below. Therefore, any of these types of syringes, and syringes that are made with the

Comprehensive Cancer Center of Wake Forest University
A Pilot Study: Open-Label Clinical Trial of CPI-613 in Patients with Advanced Bile Duct
Cancers
CCCWFU # 59212

same materials, can be used to administer CPI-613. Also, glass syringes can also be used, since glass (such as glass containers) is compatible with CPI-613 drug product.

- Norm-Ject, polyethylene barrel, polyethylene plunger, latex free (Henke Sass Wolf GMBH) syringes
- Becton Dickinson syringes
- Terumo syringes
- Monoject syringes
- Glass syringes

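### Section 7.4 bars DEHP-containing infusion sets, yet labels one of its four usable sets as not DEHP-free

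*Combined protocol and SAP*

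**What the plan says.** Everything on this point stands in Section 7.4, which covers infusion sets, syringes and bags.

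- **The reason.** Citing Study COM-003, the section warns that "CPI-613 can cause leaching of DEHP from IV infusion sets and IV bags".
- **The restriction.** It concludes that "DEHP-containing IV infusion sets, IV bags or syringes should not be used in mixing or administration of CPI-613".
- **The lead-in.** The next sentence introduces what follows as "Examples of the IV sets, IV bags and syringes that do not contain DEHP and therefore can be used in the administration of CPI-613".
- **The permission.** The infusion-set entry under that lead-in cites compatibility study COM-001 and states that "these 4 types of IV infusion sets, and IV infusion sets that are made with the same materials, can be used to administer CPI-613".
- **The label.** Four sets follow. The fourth, a polyethylene paclitaxel set (2C7558), is described as "Non DEHP-free: Polyethylene tubing with a 0.22 microfilter".

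**The concern.** The list tells staff which equipment to use when giving the drug; it is not background text. Someone who reads the fourth entry literally finds a set that the list allows and that the restriction a few lines above it bars. The text does not say which statement governs. The permission also extends to other sets made of the same materials, so the ambiguity is not confined to one catalogue number.

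If the label is accurate and the set is used, patients could be exposed to leached DEHP, a source of toxicity that is not the study drug. Safety is one of the two primary outcome measures in Section 2.2, so such a source is worth ruling out. If the label is inaccurate, nobody is exposed, but the protocol misdescribes a set that it allows.

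**Working it through.** No arithmetic applies. The check compares the statements within Section 7.4 and then looks for anything elsewhere that would settle the difference.

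**Step 1: the four sets, in the order listed.**

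| Set | Material given | DEHP statement |
|---|---|---|
| 1 (V14453) | PVC | Free of DEHP: "2 Injection Sites, DEHP-Free and Latex-Free, 15 drops/mL" |
| 2 (2C7451) | Latex | None |
| 3 (SV*S25BLS) | PVC | Free of DEHP: "0.19 mL Volume, Latex-Free, DEHP-Free" |
| 4 (2C7558) | Polyethylene | Not free of DEHP if read literally: "Non DEHP-free: Polyethylene tubing with a 0.22 microfilter" |

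The tally is 2 labelled free, 1 with no statement and 1 labelled not free: 2 + 1 + 1 = 4. This agrees with the four sets that the section says were tested.

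**Step 2: set the entries against the two governing sentences.** The restriction excludes anything containing DEHP. The lead-in says that the examples do not contain it. Sets 1 and 3 satisfy both on their own wording. Set 2 satisfies them only by virtue of the lead-in. Set 4, read literally, contradicts both. Because sets 1 and 3 carry the plain label, the different wording on set 4 reads as a contrast.

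**Step 3: does the listing itself vouch for set 4?** It does not. The permission rests on COM-001, which the reference list dates to 2006 and describes as compatibility testing with infusion sets. The restriction rests on COM-003, dated 2009, on the release of DEHP. As the protocol cites it, COM-001 supports compatibility with the drug. It is not cited as showing that DEHP is absent.

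**Step 4: does another section resolve it?** Sections 7.2 (handling), 7.3 (storage) and 7.5 (reconstitution and administration) say nothing about DEHP. The label, the list and the restriction are left standing together.

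**The case against.** The strongest reply is that the label is a slip, perhaps a merger of non-DEHP and DEHP-free. The context gives this real support. The entry is headed as polyethylene, the words after the label describe polyethylene tubing, and the entry sits under a lead-in for DEHP-free items. The title of COM-003 in the reference list also refers to polyvinyl-chloride sets and bags. A reader who takes the label at face value has, moreover, already been told not to use such a set.

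Most of this stands, and it limits the point. It does not remove it, because a slip in an operating instruction still has to be corrected and the documents do not confirm that it is one.

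Two stronger readings are tempting, and neither is supported.

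- A reader might infer that the protocol permits a set that contains DEHP, and hence that patients are exposed. The documents never state the composition of the set beyond the label. Exposure would require that the set does contain DEHP, that the site chooses it from the four, and that staff pass over the restriction. None of these is established.
- A reader might size the problem from the dosing schedule: 5 infusions in the pre-Cycle 1 week and 6 in each of 12 cycles, 5 + 6 × 12 = 77. That counts every scheduled infusion, not infusions given with this set. Nor is it a maximum or a common total. Cohort 1 has no pre-Cycle 1 week, which leaves 6 × 12 = 72, and Section 6.3 allows cycles beyond 12. The figure does not measure this defect and should not be used.

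**Conclusion.** The inconsistency is real as written: the label on the fourth set, read literally, cannot be squared with the restriction or with the sentence that introduces the list. The conclusion rests only on the ordinary meaning of the words and on the absence of any clarifying text. It does not assume that the set contains DEHP.

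The size of any consequence cannot be derived from the documents, which give neither the composition of the set, nor how often it is used, nor the amount of DEHP leached. If the label is a slip, the exposure from this source is nil. The sample size and the planned descriptive analyses in Section 9.0 do not change. This is a low-priority drafting correction, worth making because it concerns how the drug is given and costs almost nothing.

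**What to change.** Obtain the product specification for the fourth set (2C7558) and reconcile its label, its place on the list and the DEHP restriction in Section 7.4, so that all three agree. Which of them changes depends on what the specification shows, and that decision is for the sponsor and the investigator. In the same check, state the DEHP status of the second set (latex, 2C7451), so that all four entries carry an explicit statement.

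The cost is two specification look-ups and one or two lines of protocol text. The statistical section needs no change.
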